## D. Data Analysis

We will use Linear Mixed Models (LMMs) and Generalized Linear Mixed Models (GLMMs) to account for various levels of correlation among participants. Power for this study was based on power for the primary analysis comparing BMI outcomes at T2 between the two groups, adjusting for baseline BMI values. Such an approach is also known as a “mixed-model ANCOVA.” We will implement these models using SAS PROC MIXED and GLIMMIX, Version 9.3.

Research questions guiding the analysis of cognitive interview data for this aim are: Were there specific components of the intervention that appealed more than others? Were there any specific components which were not liked or were objectionable in anyway? Was there an age- or gender-related difference in reactions to components of the intervention?

To analyze mediating effects of self-regulation and self-efficacy on health outcomes and M/V physical activity, we will use bootstrapping techniques to determine significant relationships between the potential mediating variables and outcomes of interest.

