#### **Sample**

We conducted a careful analysis of sample size calculations for primary analysis of the primary outcome: BMI in adolescents at 6 months post intervention. As discussed further below, we will use a mixed model ANCOVA in our primary analysis. Power calculations for this approach are given by Murray. Power in a G-RCT is influenced by five factors: number of groups (schools), number of individuals in each group (adolescents in each school), similarity of outcomes within clusters (school-level intra-class correlation [ICC] for BMI), similarity of outcomes within individuals (correlation of BMI measurements on the same student over time), and percentage of the variance that can be explained by the regression model. Using data from the **Ohio Family Health Survey**, we estimate that the school-level ICC for BMI among 9th graders in Appalachian Ohio counties is 0.023. We further estimate the over-time correlation of BMI measurements is 0.70 and that adjusting for age and gender will explain approximately 30% of the variance in BMI. With these assumptions, 10 schools per condition, and 75 students per school, we will have 82% power to detect a modest intervention effect (0.2 standard deviation difference between groups). This effect size would correspond to a difference in mean BMI between groups of 1.04 kg/m^2 if the observed variation in BMI is similar to that of all Appalachian 9th graders from the Ohio Family Health Survey (mean BMI = 23.41, SD = 5.2).

With an average of 75 mentee participants per school (50% participation rate of eligible students based on our preliminary work), we estimate that a total of 1,500 9th and 10th grade participants will be recruited over 2 years (750 per year). Further, 190 older teens will be recruited to serve as peer mentors (19 per school x 10 schools) in the MBA condition, for a study total of 1,690 high school-aged children. Recruitment of mentor and mentee participants will occur during the start of the school year (September).

At the end of the academic year, we will randomly select at least 1 PBA teacher and 5 teen mentors from each school that delivered the curriculum that year to participate in cognitive interviews. These semi-structured interviews will be conducted individually and will be audio-recorded. Audio recordings will be transcribed verbatim. Each interview will last approximately 30 minutes and will be held in a private room at each school.

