#### **IV. Measurement/Instrumentation**

**Measures.** Our measures are comprised of items adapted from published studies and preliminary studies. All measures have been used with adolescents residing in rural or Appalachian settings and show acceptable psychometrics: internal consistency reliability  $\alpha$  of .75-.94; face validity, predictive validity, and content validity, and/or construct validity are established (See Table 1).

Table 1. Variables, Instruments, Reliability, Validity and Data Collection Times for the Teens

Variable from Theoretical Framework	Instrument/ Source of Data	Cronbach's Alpha	Type of Validity	Data Collection Times			Measure Used in Statistical Analysis
				Pre	3 mo	6 mo	
Demographics (potential covariates/moderators)	Demographic questionnaire	NA	NA	X			Item ratings/answers
Behavioral Outcomes	Healthy Lifestyle Behaviors Scale	.84 and ↑	Face, Content Construct	X	X	X	Total score on the Healthy Lifestyle Behaviors Scale
	Accelerometer Activity			X	X	X	7 days of daily activity
Behavioral Outcomes	Daily Lifestyle Patterns		Content, Construct	X	X	X	4-item questionnaire
Primary Health Outcomes	Body Mass Index, BMI%, Body Fat%	NA	NA	X	X	X	BMI, BMI%, Bio Electronic Impedance
Psychological Determinants	Physical Activity Outcome Expectations	.86-.97	Construct Predictive	X	X	X	Total Score on each of 8 sub-scales: relaxation, fitness, competition, social growth, social continuation, health Total Score
	Self-Efficacy for Physical Activity	85-.94	Predictive	X	X	X	
Self-Regulation	Self-Regulation for Physical Activity	.89-.95	Content and Construct	X	X	X	Total score on each 6 subscales: goal setting, self-monitoring, overcoming barriers, time management, self-reward, planned support
	Social Support	.75-.88	Face and Construct	X	X	X	Total Score
Environmental Determinants	Perceived Environment for Physical Activity	Test-retest (59%-74%)	Construct	X	X	X	Total score on each of 1 subscale: neighborhood

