**Table 5: Data Procedures and Process**

Time	Process:	(Data Provided By)	Team Member
YEAR 1			
	Finalization of data collection protocols Finalization of participating schools to Waves 1 or 2 Training of PD and RAs: protocols, use of accelerometers Randomization of Wave 1 schools to either intervention or comparison	[name] & [name] [name] & [name] [name] & [name] ([name])	
WAVES 1,2			
Consent	Consent/Accent of Peer Mentors and School Participants	[name] or [name]	
End of Recruitment	1. Assignment of identification numbers to subjects, mentors, and teachers 2. Demographic Questionnaire (Peer Mentor, Subjects)	[name] Team	
Baseline (T 1 )	Subject Survey Questionnaire: Self-Report Height, weight, BEI Accelerometer – one week of data a Health Behaviors Questionnaire: (Subjects) (Subjects) (Teachers, Peer Mentors, Subjects) (Peer Mentors, Subjects)	Team	
T 1 : Follow-Up	Collection of accelerometer data (7 days)	Team	
Weekly	Debriefing sessions: observations and notations: mentors and teachers Measures of Fidelity (mentors and teachers) Data Interim Reports	[name] & [name]	
Monthly	Measures of Fidelity (mentors and Teachers)	[name] & [name]	
3 Months Post Intervention (T 2 )	Subject Survey Questionnaire: Self-Report Height, weight, BEI Accelerometer – one week of data a Health Behaviors Questionnaire (Subjects) (Subjects) (Teachers, Peer Mentors, Subjects) (Peer Mentors, Subjects)	Team	
T 2 : Follow-Up	Collection of accelerometer data (7 days) Reinforcement (Booster) Session	Team	
6 Months Post Intervention (T 3 )	Survey Questionnaire: Self-Report Accelerometer – one week of data a Health Behaviors Questionnaire (Subjects) (Teachers, Peer Mentors, Subjects) (Peer Mentors, Subjects)	RA (blinded to group)	
T 3 : Follow-Up	Collection of accelerometer data	Team	

BEI = bio-electronic impedance; aAccelerometer data collected over 3 weeks (1/3 of subjects each week to wear for 1 week)

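### The primary BMI time point is 6 months in the sample-size section but T2 (3 months) in the analysis section, and the 6-month row of Table 5 lists no height or weight

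*Combined protocol and SAP*

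**What the plan says.** - **Sample (section III.A).** The sample-size calculation is for the "primary analysis of the primary outcome: BMI in adolescents at 6 months post intervention", using a mixed-model ANCOVA.
- **Section D, Data Analysis.** Power is said to rest on the "primary analysis comparing BMI outcomes at T 2 between the two groups, adjusting for baseline BMI values", also called a mixed-model ANCOVA.
- **Table 5, labels.** T1 is baseline. The later visits are headed "3 Months Post Intervention (T 2" and "6 Months Post Intervention (T 3", each with a closing bracket.
- **Table 5, content.** The T1 and T2 rows read "Subject Survey Questionnaire: Self-Report Height, weight, BEI Accelerometer – one week of data", followed by the health behaviors questionnaire. The T3 row reads "Survey Questionnaire: Self-Report Accelerometer – one week of data", followed by the same questionnaire, with no height, weight or bio-impedance.
- **Table 1 (section IV).** The row for "Body Mass Index, BMI%, Body Fat" percentage is marked at baseline, 3 months and 6 months.
- **Section B, Detailed Study Procedures.** Anthropometric data are to be taken at T1, T2 and T3. The same section sends the reader to Table 5 for the data collection plan.

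**The concern.** Two sections each claim to describe the one primary analysis and its power, and they place it three months apart. This is not a primary and a secondary analysis described in different places.

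The visits also answer different questions. Table 5 puts a booster session after the T2 measurements, so T3 reflects the booster and T2 does not.

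If the choice is left open until data are in hand, it can follow the results. Separately, a field team working from Table 5 would not weigh or measure students at 6 months, and the outcome named in the Sample section would not exist. The multiple imputation described under Internal Validity cannot credibly replace an outcome that nobody has at that visit.

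**Working it through.** **1. Can T2 mean 6 months?** No. Baseline is T1 throughout and no T0 is used. Table 5 labels T2 as 3 months and T3 as 6 months. The Internal Validity section speaks only of pretest and posttest, so it does not settle the matter.

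**2. Is the measurement missing from Table 5, or lost in text extraction?** Count the items in each row against the data-provider entries:

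| Row | Items | Provider entries | Height, weight, bio-impedance |
|---|---|---|---|
| T1 | 4 | 4 | listed |
| T2 | 4 | 4 | listed |
| T3 | 3 | 3 | not listed |

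The entry absent at T3 is one of those for subjects, which fits the absent anthropometry line. Items and providers still match, so a partial loss of text is unlikely. Loss of a whole printed line cannot be excluded by this count.

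**3. Does the stated power show which time point was meant?** Inputs from the Sample section: g = 10 schools per arm, m = 75 students per school, ICC = 0.023, over-time correlation r = 0.70, effect 0.2 SD. The effect in BMI units is 0.2 × 5.2 = 1.04 kg/m², as stated. Assumptions: two-sided alpha of 0.05 (not stated) and a t test on 2(g − 1) = 18 df.

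- Variance of the difference in SD units = f × 2[1 + (m − 1)ICC]/(mg) = f × 2(1 + 74 × 0.023)/750 = f × 2 × 2.702/750 = 0.007205 f.
- The residual factor f is not given. With f = 2(1 − r) = 0.60, SE = √(0.007205 × 0.60) = 0.0658 and power is 82.0%, matching the stated 82%.
- With f = 1 − r² = 0.51, the usual factor for ANCOVA on baseline, SE = 0.0606 and power is 87.7%.

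The time point could enter only through r, and the documents do not tie 0.70 to 3 or 6 months. Over an assumed range of r:

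| r | Power, f = 2(1 − r) | Power, f = 1 − r² |
|---|---|---|
| 0.60 | 70.0% | 79.5% |
| 0.70 | 82.0% | 87.7% |
| 0.80 | 93.9% | 95.8% |

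The 82% can be reproduced, but it does not identify the visit.

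**4. Students affected if Table 5 is followed.** 20 schools × 75 = 1,500 enrolled; 1,500 × 0.80 = 1,200 expected at follow-up.

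**5. Error rate if both visits are tested at 5% and the significant one is reported.** For independent results, 1 − 0.95² = 9.75%. For two correlated standard normal statistics, the chance that at least one exceeds 1.96 in absolute value is:

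| Correlation of the two statistics (assumed) | Error rate |
|---|---|
| 0 | 9.75% |
| 0.41 | 9.3% |
| 0.50 | 9.1% |
| 0.70 | 8.3% |
| 0.90 | 7.0% |

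The 0.41 is the correlation of T2 and T3 BMI given baseline if all three pairwise correlations are 0.70: (0.70 − 0.49)/(1 − 0.49) = 0.41.

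**The case against.** The best defence is that the Sample section is the only place that defines the primary outcome together with its time, and that it points forward to the analysis section. On that reading there is one analysis, and T2 in section D is a wrong subscript. The measurement section supports this by justifying raw BMI on the ground that the trial is long-term. Table 1 and section B both schedule BMI at 6 months, so the measurement is not absent from the plan as a whole.

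Much of this stands. A slip is the likeliest explanation, 6-month BMI is missing from one schedule rather than from all of them, and the plan nowhere proposes to pick the better result. The count of 1,500 and the 9.75% are upper limits: the first assumes staff follow Table 5 against Table 1, the second assumes independent results and that both tests are run. The omission from the T3 row is also less certain than the conflict over the time point, because the table has been flattened.

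Table 5 describes only the T3 research assistant as blinded to group and says nothing either way about the team at T2. That is worth clarifying, but it is an argument from silence and the finding does not rest on it.

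None of this removes the contradiction. The section that governs the analysis names T2, and the table that governs fieldwork omits the T3 measurement. A reader who follows those two literally gets a different trial from the one in the Sample section.

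**Conclusion.** The concern holds and must be fixed. The conflict over the primary time point is certain from the text. The Table 5 omission is probable, and it conflicts with Table 1 and section B.

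At worst, the declared primary outcome goes unmeasured in up to 1,500 students (about 1,200 at the planned 80% retention), and 3-month BMI takes its place as the primary test. If both visits are measured and the choice stays open, selecting the significant result puts the error rate above 5% and at most at 9.75%. It is roughly 7.0% to 9.3% for assumed correlations between 0.90 and 0.41. The power calculation neither resolves the question nor depends on it as written.

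**What to change.** 1. **Name one primary time point and use it everywhere.** T3 (6 months) has the better support: the Sample section, the reason given for using raw BMI, and the Background's remark that longer-term follow-up is lacking. In that case, change section D to BMI at T3, adjusted for baseline BMI, and label BMI at T2 as secondary. If T2 is really intended, change the Sample section instead and make T3 secondary.
2. **Reconcile Table 5 with Table 1 and section B.** Add height, weight and bio-impedance for subjects to the T3 row, under the blinded research assistant already listed there. State whether the T1 and T2 measurement teams are blinded.
3. **Tie the over-time correlation of 0.70 to the chosen interval** in the Sample section.
4. **Date the correction** and make it before any follow-up BMI is compared by arm. If that point has passed, say so.

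The cost is a few words in section D or the Sample section and one line in Table 5. Table 1 and section B already assume the 6-month measurement, and section B puts anthropometry at 10 to 15 minutes per student, so no new procedure is added.

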## **Participant Recruitment and Retention**

Nine school districts from 9 rural Appalachian Ohio counties have agreed to participate; an excess of 10 schools needed for Wave1. Wave 2 schools will be recruited during Year 1 of the study (with amendment to IRB protocol once letters of support are received). Peer mentors will be recruited based on interest in working with peers, supporting others, and striving to cultivate their own health-supportive behaviors. Eleventh and 12th graders attending the target high school at the study's start will be eligible to participate as mentors if they are not expected to move from the participating school before the conclusion of the study; can speak English; and are recommended by a teacher, school advisor, or counselor. Teens interested in serving as mentors will complete an application form; selection will be based on: study needs, motivation to serve, and recommendations. Teen mentors with a BMI (for age and gender) above the 85th percentile or below the 5th percentile at the start of the study will be excluded because of concerns about those not classified as having a healthy weight serving as role models for healthy lifestyle behaviors. These exclusionary criteria will be clear in recruitment materials so those excluded understand why. All teen mentors will attend the same school and reside in the same local community as study participants. Each peer mentor will be assigned up to 4 adolescents (2 per session; 2 possible sessions each week); we will recruit 19 peer mentors per school. We will attempt to match mentors and mentees by gender.

School health teachers at participating schools will provide the comparison delivery method. With approximately 25 students per classroom, we anticipate 3 classrooms to participate in each comparison school. Based on preliminary studies, an 80% retention rate is expected, resulting in 82.5% power to detect a modest intervention effect. To aid retention of subjects, monetary incentives at each data collection time-point and booster kits for use during the summer months will be provided. In addition, attendance will be taken at all sessions; the PI will contact all subjects missing a session within 48 hours.

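### The analysis section names only baseline BMI as a covariate for the primary comparison; the age and gender adjustment used for power is not carried over, and wave is in no model (minor, cheap to fix)

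*Combined protocol and SAP*

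**What the plan says.** Section D (Data Analysis) compares BMI "between the two groups, adjusting for baseline BMI values" and calls this a mixed-model ANCOVA. No other covariate is named there. Section C (Internal Validity) describes intention to treat, multiple imputation, standard errors and degrees of freedom, but lists no covariates.

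The Sample text names the same type of model. It counts the "percentage of the variance that can be explained by the regression model" among five factors that drive power, and assumes that "adjusting for age and gender will explain approximately 30% of the variance in BMI". The result is: "10 schools per condition, and 75 students per school, we will have 82% power to detect a modest intervention effect". Table 1 in section IV has a row labelled "Demographics (potential covariates/moderators", which leaves their use open.

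On waves, Sample says that 9th and 10th "grade participants will be recruited over 2 years (750 per year". Table 5 lists, for Year 1, "Randomization of Wave 1 schools to either intervention or comparison". Participant Recruitment and Retention says that 10 schools are needed for Wave 1 and that "Wave 2 schools will be recruited during Year 1 of the study". No model statement mentions wave.

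**The concern.** The power statement and the analysis section describe the adjustment differently. If age and gender are part of the planned model, the analysis section should say so. If they are not, the stated 82% may rest on an adjustment that will not be made. Table 1's wording also leaves the choice open until outcomes have been seen.

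Wave appears to define the set within which schools are allocated. If outcomes differ between the two school years after baseline BMI is taken into account, a model without wave puts that difference into the school-level error. The arm comparison is then tested against an inflated error term, and some power is lost.

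**Working it through.** **Inputs (Sample):** ICC 0.023; over-time correlation 0.70; 30% of variance from age and gender; 10 schools per arm; 75 students per school; effect 0.2 SD; SD 5.2 kg/m2. Participant Recruitment and Retention adds 80% retention (0.80 × 75 = 60 per school) and a power of 82.5%. **Assumed:** two-sided 5%, since no alpha is stated.

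**Formula.** In SD units, the variance of a school mean is v = a(1 − 0.023)/m + b(0.023), where a and b are the shares of student-level and school-level variance left after adjustment. The standard error of the arm difference is √(2v/10), tested by t on 2 × (10 − 1) = 18 df (noncentral t).

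**Reproducing the plan's power.** The documents do not show how 0.70 and 30% enter, so four forms were tried.

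| Form | a | b | m = 75 | m = 60 |
|---|---|---|---|---|
| A: 1 − 0.70² at both levels | 0.51 | 0.51 | 87.7% | 84.8% |
| B: 2(1 − 0.70) at both levels | 0.60 | 0.60 | 82.0% | 78.7% |
| C: B's student term × 0.70; school 0.70 | 0.42 | 0.70 | 82.1% | 79.7% |
| D: A's student term × 0.70; school 0.70 | 0.357 | 0.70 | 83.5% | 81.5% |

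For example, B at m = 75: v = 0.60 × 0.977/75 + 0.60 × 0.023 = 0.02162; standard error 0.0658; 0.2/0.0658 = 3.04; power 82.0%.

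B, C and D come near the stated 82%. C and D use the 30%; B does not. Of these three, only D is also within 2 points of the 82.5% stated at 80% retention. That favours a calculation that included age and gender but does not prove it: a formula of this kind cannot give more power at 60 per school than at 75, so the two stated figures cannot both be exact for it.

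Removing the 30% from C gives (a, b) = (0.60, 1) and 67.4%. Removing it from D gives (0.51, 1) and 69.0%. With b = 1, baseline BMI explains none of the between-school variance.

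**What age and gender add once baseline BMI is in the model.**
- Full overlap with baseline BMI: 0 points.
- The same 30% at both times, 0.70 the total correlation: the residual is 0.70 − (0.70 − 0.30)²/0.70 = 0.471, against 0.51 with baseline BMI only. Power rises from 87.7% to 90.0% (75 per school, +2.4 unrounded) or from 84.8% to 87.4% (60 per school, +2.6).
- 0.70 the correlation left after age and gender: the total correlation is 0.30 + 0.70 × 0.70 = 0.79. The residual falls from 1 − 0.79² = 0.376 to 0.70 × 0.51 = 0.357. The gain is 0.9 points (75) or 1.1 (60).

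**Wave.** Assumptions: 10 schools per wave split 5:5, and a between-wave gap g that remains after baseline adjustment and is additional to the ICC. Each school mean then sits g/2 from its arm mean, so the error sum of squares gains 20 × (g/2)² = 5g². Without wave, the error term is noncentral chi-square on 18 df with noncentrality 5(g/5.2)²/v. With wave, it is central on 20 − 2 − 1 = 17 df. Form A, 75 per school (v = 0.01837):

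| Gap (kg/m2) | Power without wave | Power with wave | Change (points) | Type I error without wave |
|---|---|---|---|---|
| 0 | 87.7% | 87.5% | −0.2 | 5.0% |
| 0.1 | 87.6% | 87.5% | −0.1 | 4.9% |
| 0.2 | 87.2% | 87.5% | +0.3 | 4.8% |
| 0.3 | 86.6% | 87.5% | +0.9 | 4.5% |
| 0.5 | 84.6% | 87.5% | +2.8 | 3.8% |

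Changes are taken from unrounded values. Over forms A to D and both school sizes, the lost degree of freedom costs 0.22 to 0.28 points, the gain at a gap of 0.5 is 2.8 to 3.0 points, and break-even lies at about 0.14 kg/m2.

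**The case against.** The quoted sentence explains the basis for power and why the model is called an ANCOVA; it is not a closed covariate list. Sample names the same model and gives the age and gender adjustment, so the two sections can be read as one model with all three covariates. Form D's fit to both stated powers supports that reading. This stands. That the model adjusts for baseline BMI and nothing else is inferred from silence, and a reader should not conclude that age and gender are excluded. What remains is that the section governing the analysis does not say they are included, and Table 1 calls them only potential.

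On wave, the documents give no difference between waves. Each student's own baseline BMI already removes ordinary level differences, and below about 0.14 kg/m2 the extra term loses a little power. Separate randomisation of Wave 2 and an even split within each wave are inferences. All of this stands, and it limits the wave part to a low-cost improvement.

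A reader might infer bias or an inflated type I error from the omission of wave. The documents do not support that: with even allocation, the estimate is unbiased and type I error is at or below 5%. Nothing in the documents suggests an uneven split.

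**Conclusion.** The point holds as a minor matter of efficiency and consistency. Section D names baseline BMI only, does not carry over the age and gender adjustment that Sample uses for power, and leaves wave out of the model. On the plan's inputs, age and gender added to baseline BMI are worth about 0 to 2.6 power points, depending on overlap and on what the 0.70 means. Omitting wave makes the test conservative by an unknown and possibly negligible amount: about 0.3 to 2.8 power points and a type I error of 4.8% to 3.8%, if the residual gap is 0.2 to 0.5 kg/m2 and the split is 5:5.

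The 67.4% and 69.0% figures could tempt a reader to infer a loss of about 15 points. They are an accounting lower bound for two possible power formulas in which baseline BMI explains no between-school variance. They are not what fitting the model in section D would be expected to cost; form A, which uses baseline BMI and no age or gender, gives 87.7% at 75 per school and 84.8% at 60.

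**What to change.** In section D, state the primary model as: BMI at the primary time point = arm + baseline BMI + age + gender + wave (randomisation set) as fixed effects, with a random intercept for school and 17 school-level degrees of freedom. Use the same terms in the multiple imputation model in section C. State whether Wave 2 schools are randomised as their own set and whether allocation is even within each wave.

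This takes one or two sentences and no new data: baseline BMI, age and gender are collected, and wave is known by design. The downside is one school-level degree of freedom, about 0.2 to 0.3 power points if the waves do not differ.

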## **Research Protocol : A Skill-Based RCT for Physical Activity Using Peer Mentors**

### **I. Objectives/Aims of the Study:**

The long-term goal of this study is to positively impact the physical activity patterns to improve health outcomes including the high rates of obesity in Appalachian teens. For this RCT, we will train peer mentors to deliver the culturally appropriate intervention and provide social support that is critical for facilitating and sustaining health behavior change. Our objective is to compare the efficacy of an innovative healthy lifestyle skills mentoring program (*Mentored Planning to be Active [MBA]*) to a teacher led program (PBA) for increasing physical activity in Appalachian high school teens. Our specific aims are:

**Aim 1:** Compare the efficacy of peer-led delivery (**MBA**) to teacher-led delivery (**PBA**) on health outcomes.

- a. Examine the relationship between health behaviors (sugar sweetened beverage consumption, sleep patterns, and health outcomes (body mass index, body fat at baseline)

**Aim 2:** Compare the efficacy of peer-led delivery (**MBA**) to teacher-led delivery (**PBA**) on physical activity behavior outcomes of Appalachian teens.

**Aim 3:** Examine the behavioral impact of the mentoring approach on teen mentors and teachers.

**Aim 4:** Examine the usefulness, ease of use, general satisfaction, and suggested refinements of the approach by the teen mentors and teachers.

**AIM 5:** Determine if self-regulation skills and exercise self-efficacy mediate the relationship between health outcomes and moderate/vigorous physical activity.

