### **III. Procedures:**

#### **A. Research Design**

Our approach is to randomize participants to one of two groups: (1) intervention: Peer Mentoring (MBA), and (2) comparison: Teacher-Led (PBA). We will test the hypothesis that, compared to delivery by teachers in a classroom setting (usual care), an innovative delivery format of PBA by local peer mentors (trained 11th and 12th grade teens) will promote the adoption of healthier physical activity and regular exercise among 9th and 10th grade teens not engaged in organized sports by combining (a) peer mentoring by trained high school students to younger adolescents with (b) a tailored self-regulation lifestyle program. We propose a **group-randomized controlled trial** (G-RCT) to evaluate mentored delivery of a school-based intervention to improve physical activity behaviors and health outcomes among high school students in Appalachian Ohio. G-RCTs are characterized by random assignment of identifiable social groups (rather than individuals) to study conditions, with measurements taken on members of those groups to assess the impact of the intervention.

Prior to the intervention (baseline data), we plan to complete a sub-analysis of the relationship between health behaviors from lifestyle behavioral scale (sleep patterns reported and sugar sweetened beverage consumption rates and measured body mass index and body fat percentage).

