### **Psychosocial Determinants**

**Outcome Expectations for Physical Activity:** The outcome expectancy values instrument in this study assesses outcome expectations and their associated expectancies for physical exercise by requesting information on six dimensions: relaxation, fitness, competition, social growth, social continuation, and health. Each of the eight dimensions is measured by five items. Previous studies demonstrated internal consistency, reliability coefficient ranging  $\alpha = 0.86-0.97$  when used with Appalachian teens. Construct validity has also been demonstrated through three confirmatory factor analyses using data from our previous work.

**Self-Efficacy for Physical Activity:** Self-efficacy will be measured using a previously developed instrument with 14 items. The instrument has demonstrated predictive validity for boys and girls: 0.23 and 0.27 Re-test reliability of this scale has been reported to be 0.82. This instrument has been refined by adding three additional items and altering the response scale from dichotomous to a five-point Likert-type scale, with internal reliability consistency ranging  $\alpha = .85-.94$ .

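### The Aim 5 mediation analysis states a test of mediator-outcome relationships only; it should test an indirect effect with a named exposure, order and time points

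*Combined protocol and SAP*

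**What the plan says.** Section I sets Aim 5 as: "Determine if self-regulation skills and exercise self-efficacy mediate the relationship between health outcomes and moderate/vigorous physical activity". The two constructs stand between health outcomes and MVPA. Neither end is designated the exposure, and study condition (MBA or PBA) is not mentioned.

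Section D (Data Analysis) gives the matching analysis in one sentence. It opens "To analyze mediating effects of self-regulation and self-efficacy on health outcomes and M/V physical activity" and continues "we will use bootstrapping techniques to determine significant relationships between the potential mediating variables and outcomes of interest". The opening clause lists health outcomes and MVPA together as things the mediators act on. The operative clause names only the mediator-outcome relationship.

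No other section sets out a path from an exposure to the mediators, an indirect effect, the visit that supplies each variable, or how the bootstrap handles schools. Table 1 and Table 5 show when data are collected, not which visit enters which path.

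**The concern.** Mediation needs two legs: the exposure must move the mediator, and the mediator must move the outcome given the exposure. The indirect effect is the product of the two. A test of the second leg alone can be significant when the first leg is absent. If the exposure is left out of the model, it can also be significant when the second leg is absent, because the exposure drives both variables.

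Self-efficacy and self-regulation would be expected to correlate with activity in most teenage samples, so a significant result is likely before any question of mediation arises. Aim 5 could then be reported as confirmed although the stated test had not addressed it. Because the order of the two ends is open, several models also fit the text, and the choice among them could be made after the data are seen.

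**Working it through.** The plan gives no sample size, power or error rate for Aim 5, so there is no figure of its own to reproduce. The check asks how often the stated test is significant when nothing is mediated.

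**Inputs from the plan**
- "10 schools per condition, and 75 students per school" (Sample): 20 × 75 = 1,500 students.
- "an 80% retention rate is expected" (Participant Recruitment and Retention): 0.80 × 1,500 = 1,200, or 60 per school.
- School ICC 0.023, which the plan gives for BMI only.

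**Assumptions**
- Mediator-outcome slopes of 0.23 and 0.10 on a standardised scale. The upper value is borrowed from the self-efficacy scale: "The instrument has demonstrated predictive validity for boys and girls: 0.23 and 0.27". It is only a convenient value, for reasons given in the objection. No comparable figure is given for self-regulation.
- Mediator ICC 0.01 to 0.05; exposure and outcome ICC 0.023; 95% intervals.

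**1. Formula check of the stated test (clustering ignored).** With z = atanh(r) × √(n − 3) and n = 1,200, √1,197 = 34.6.
- r = 0.23: z = 0.2342 × 34.6 = 8.10, power above 99.9%.
- r = 0.10: z = 0.1003 × 34.6 = 3.47, power = Φ(3.47 − 1.96) = 93.5%.
- Correlation detected with 80% power: tanh(2.80/34.6) = 0.081.

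**2. No exposure-to-mediator path (true indirect effect zero).** Simulation of 20 schools × 60 students, with a student-level exposure unrelated to the mediator, a student bootstrap of 600 draws and 600 replicates per row (Monte Carlo SE about 0.9 points near 5%):

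| Slope | Mediator ICC | Mediator-outcome test significant | Indirect-effect test significant |
|---|---|---|---|
| 0.23 | 0.01 | 100% | 5.3% |
| 0.23 | 0.023 | 100% | 4.5% |
| 0.23 | 0.05 | 100% | 6.2% |
| 0.10 | 0.01 | 92.8% | 5.5% |
| 0.10 | 0.023 | 91.8% | 6.0% |
| 0.10 | 0.05 | 92.7% | 5.2% |

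Clustering matters little here. The approximate variance inflation for an association between two student-level variables is 1 + (60 − 1) × 0.023 × 0.05 = 1.07.

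**3. No mediator-to-outcome path.** Exposure-to-mediator path 0.3, direct exposure-to-outcome path 0.3, n = 1,200, unclustered, 200 replicates. The stated test was significant in 79.5% and the indirect-effect test in 5.5%. Formula check: the induced correlation is 0.09/1.09 = 0.083, z = 0.0828 × 34.6 = 2.86, power = Φ(2.86 − 1.96) = 82%, which agrees within simulation error.

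**4. True mediation (all three paths 0.2).** Both tests were significant in 100%.

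Under these assumptions the stated test is significant in most trials in all three situations. The indirect-effect test separates the third from the first two.

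**5. Time points.** Table 1 marks the mediators, accelerometry, BMI and body fat at baseline, 3 and 6 months. In Table 5 the T1 and T2 rows list height, weight and impedance between the survey and the accelerometer. The T3 row reads "Survey Questionnaire: Self-Report Accelerometer", with nothing between. T1 and T2 list four items and four data sources, and T3 lists three of each, so the gap does not look like a lost table cell. The two tables therefore disagree on whether a 6-month health outcome is collected.

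**The case against.** The strongest reply is that the sentence should be read whole. It declares a mediation analysis, and bootstrapping is a common way to form an interval for an indirect effect, so an indirect-effect test may well be what was meant. Aim 5 names both ends of the relationship; only their order is missing. There are also hints of order: section I's long-term goal runs from activity to health, and Table 1 labels self-efficacy a determinant and activity a behavioural outcome. Finally, the simulation illustrates a definition. It does not show what the analysts would run.

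Much of this stands. A reader might infer that the plan cannot answer Aim 5 at all. The documents do not support that, because the opening clause states a mediation purpose. But intent does not settle the model. The hints point different ways: the long-term goal makes activity the exposure, while Table 1 puts the mediators upstream of activity. The only test in writing is still the one-leg test.

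Two further inferences should be resisted.
- **The 0.23 and 0.27 as correlations with activity.** The criterion is not stated. The same paragraph says the scale was later extended and its response format changed. The reference cited is listed in the bibliography as a study of self-efficacy for resisting social pressure to smoke. The conclusion does not need these values, since a slope of 0.10 leads to the same place.
- **Arm as the exposure, with a student-level bootstrap.** Resampling students would then give false-positive rates of 2 × [1 − Φ(1.96/√(1 + 74 × ICC))] = 14% to 37% for ICC 0.01 to 0.05. Section A describes the intervention as "peer mentoring by trained high school students to younger adolescents with (b) a tailored self-regulation lifestyle program", which makes arm a plausible exposure, but neither Aim 5 nor the analysis sentence names it. No section proposes resampling individual students, and section D opens by committing to mixed models for correlated participants. These rates are not a finding against the plan.

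**Conclusion.** The point holds as a mismatch between Aim 5 and the test written for it. Followed literally, the test would be significant in about 92-100% of trials with no mediation, against about 5-6% for an indirect-effect test. This rests on 1,200 students, assumed slopes of 0.10 to 0.23, and an exposure unrelated to the mediator. The exact percentages depend on those assumptions. That the stated test cannot separate mediation from no mediation does not.

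The matter should be corrected before analysis, but it is confined to Aim 5. The primary BMI comparison does not depend on it.

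**What to change.** In Aim 5 and section D, state the same exposure, mediator, outcome, direction and time points, and say which of BMI, BMI% or body fat% is the health outcome. Replace the mediator-outcome test with a bootstrap interval for the indirect effect, from models with a school random effect and with resampling that respects schools. Label the analysis observational.

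The sponsor should choose the direction:
- **Activity to health**, which follows section I's rationale. If the outcome is a T3 health measure, first reconcile Table 1 with Table 5's T3 row.
- **T1 health outcome, T2 mediator, T3 MVPA**, with T1 mediator and T1 MVPA as covariates. This runs against section I's rationale but uses only data scheduled in both tables.

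Add an arm-to-mediator-to-outcome analysis only if the sponsor confirms that arm is an exposure. It should be separate and use school-level inference (20 schools in two arms, 18 degrees of freedom).

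The cost is rewording one aim and one analysis sentence, plus modest programming. No new data are needed for the second order; for the first, that depends on the T3 reconciliation. The downside is that an indirect-effect test will be significant less often than the test now written.
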